12.1 Sample Size Justification

For the trial to be successful, the primary efficacy endpoint must be adequately powered.

For the primary efficacy endpoint to be met, the proportion of the ITT analysis population that responds to therapy must be statistically significantly greater than 50%. A responder is defined as a subject who has an IPSS improvement $\geq 30\%$ post-treatment, as compared to baseline.

The required sample size for this endpoint was calculated based on the following assumptions:

- One-sample exact binomial hypothesis test of proportions,
- Type I error of 0.025, one sided,
- Statistical power of 90%, and
- Population responder rate of at least 67.5%.

The responder rate in the Rezūm II trial was 77.9% (106/136). A population rate of at least 67.5% is selected as a conservative assumption for the responder rate in the Rezūm XL trial based on the lower bound of a two-sided 99% confidence interval for the responder rate in the Rezūm II trial. Based on these assumptions, a sample size of at least 88 intention-to-treat subjects is required for analysis.

Additional subjects may be screened since some subjects that consent may exit the study without being enrolled (e.g. due to withdrawal of consent or not meeting eligibility criteria).

12.2 Primary Safety Endpoint - Post Procedure Device Related Serious Complications:

This safety endpoint will be to demonstrate that the composite rate of post procedure device related serious complications at 6 months is acceptably low.

The following hypothesis will be tested in a one-sided exact binomial test at the 5% significance level.

$$H_0: P_{\text{Rezūm6}} \geq 12\%$$

$$H_1: P_{\text{Rezūm6}} < 12\%$$

Where:

$P_{\text{Rezūm6}}$ is the proportion of subjects experiencing one or more safety composite events within 6 months post-procedure. The safety endpoint is a composite of the four types of events listed below.

Device-related serious complications for this endpoint are defined as:

- Device perforation of the rectum or GI tract
- Device related formation of fistula between the rectum and urethra
- Permanent damage to the bladder, trigone or ureteral orifices requiring intervention
- Grade 2 hydronephrosis

The adverse events listed above will be adjudicated by the clinical events committee (CEC) for this endpoint. With a sample size of 88 subjects, a performance goal of 12% requires that no more than 5 subjects (5.7%) experience a device-related serious complication in order for this endpoint to be met.

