9.4.2 Exclusion Criteria

Urology

1. Any prior invasive prostate intervention (e.g., “Radiofrequency” thermotherapy, balloon, microwave thermotherapy, “Prostatic Urethral Lift”, “Transurethral Resection”, or laser) or other surgical interventions of the prostate.
2. Undergone a prostate biopsy within 60 days prior to the scheduled treatment date or has an imminent need for surgery.
3. Verified acute bacterial prostatitis within last 12 months documented by culture.
4. Active or history of epididymitis within the past 3 months.
5. Urethral strictures, bladder neck contracture, unusual anatomy or muscle spasms that would prevent the introduction and use of the Rezūm device.
6. Diagnosed bladder, urethral or ureteral stones or active stone passage in the past 6 months, provided that stones that are known to be in the kidney and have been stable for a period exceeding 3 months are permissible.
7. Subject interested in maintaining fertility.
8. Use of the following medications where the dose is not stable (stable dose defined as the same medication and dose in the last three months):
 - a. Beta-blockers;
 - b. Anticonvulsants;
 - c. Antispasmodics;
 - d. Antihistamines;
 - e. Alpha blockers for BPH and anticholinergics or cholinergics;
 - f. Type II, 5-alpha reductase inhibitor (e.g., finasteride (Proscar, Propecia));
 - g. Dual 5-alpha reductase inhibitor (e.g., dutasteride (Avodart));
 - h. Estrogen, drug-producing androgen suppression, or anabolic steroids;
 - i. PD5 Inhibitors (e.g., Viagra, Levitra or Cialis)
9. Subjects who have had an incidence of spontaneous urinary retention either treated with indwelling transurethral catheter or suprapubic catheter 6 months prior to baseline. A provoked episode now resolved is still admissible.
10. Evidence of atonic neurogenic bladder evaluated by a baseline urodynamic assessment.
11. Visible hematuria with subject urine sample without a known contributing factor.
12. Presence of a penile implant or stent(s) in the urethra or prostate.
13. Active urinary tract infection by culture within 7 days of treatment or two documented independent urinary tract infections of any type in the past 6 months.

Gastroenterology

14. Previous pelvic irradiation or radical pelvic surgery.
15. Previous rectal surgery (other than hemorrhoidectomy) or known history of rectal disease.

Nephrology

16. Compromised renal function defined as serum creatinine > 2.0 mg/dl.
17. Hydronephrosis (Grade 2 or higher).

Oncology

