11.7 Retroperitoneal Ultrasound (Renal and Bladder)

A retroperitoneal ultrasound of the abdomen and pelvis will be performed to assess the patients' urinary tract integrity at pre-procedure baseline, 2 weeks (as applicable) and again at their 6 week follow-up appointment. These retroperitoneal ultrasound imaging studies will be used to determine the study's satisfaction of the primary safety endpoint, in particular the presence of permanent damage to the bladder, trigone, or ureteral orifices. The written request for sonographic examination will include sufficient information directing the examiner to allow for appropriate performance of the ultrasound focusing on the primary safety endpoint criteria listed above. Retroperitoneal ultrasound guidelines (urinary tract and bowel):

Kidney Assessment

- Kidney examination should include transverse and long-axis (sagittal or coronal) views
- Assessment of the cortices and renal pelvises should be made
- The maximum length of each kidney should be recorded
- For vascular kidney examination, Doppler ultrasound can be utilized to assess renal arterial and venous patency and suspected renal artery stenosis
- The kidneys and perirenal regions should be assessed for abnormalities
- Measurements should be taken of any abnormalities

Bladder Assessment

- For examination of the complete urinary tract, transverse and longitudinal (sagittal or coronal) images of the distended urinary bladder should be included if possible
- Abnormalities of the bladder wall or lumen should be noted

Bowel Assessment

- Evaluation of the bowel for wall thickening, dilatation, muscular hypertrophy, masses, vascularity, and other abnormalities can be made
- Identification of bowel perforations or fistulas should be reported

Any site reported abnormalities present on the 2 week (if abnormal BUN or Creatinine) or 6-week ultrasound that were not present at baseline will be reviewed as potential device-related serious complications and a final adjudication will be made by the Clinical Events Committee. The retroperitoneal ultrasound will be used in conjunction with TRUS to adjudicate the potential complications.

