12.6 Other Analyses

Adverse events, protocol deviations and device malfunction will be tabulated and included in the analysis. Descriptive statistics will be used in reporting these outcomes.

13 Definition of Study Success

The study will be declared a success if the primary efficacy and safety endpoints are met.

14 Definition of Adverse Event(s)

For purposes of this study, an AE is defined as any adverse change (i.e., *de novo* or preexisting condition) from the subject's baseline medical condition(s) occurring during the course of the study. For the purpose of AE documentation, the start of the study is defined as any time after the treatment has been initiated.

Subjects must be monitored from the start of the study, and throughout the duration of the study, for any and all AEs, including those observed as well as those reported by the subject. All AEs are to be documented by the investigator on the appropriate CRF. All AEs will remain under medical supervision until the Investigator deems the AE to be resolved, returned to baseline or stabilized at a new level no longer requiring medical supervision.

All AEs will be recorded in the CRF whether considered procedure-related or not, and will be classified as described in section 14.7.

Pre-existing conditions will not be reported as an AE unless there is an adverse change in that condition. Any AE which resolves and then recurs will be reported as a separate AE.

An AE may be volunteered spontaneously by the subject or discovered as a result of questioning or physical examination by an investigator or study staff.

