14.11 Independent Review of Retroperitoneal Ultrasound (renal and bladder)

An independent reviewer will review all baseline, 2 week (if applicable) and 6 week retroperitoneal ultrasounds to assess for any unreported device-related serious complications defined as:

- Device perforation of the rectum or GI tract

- Device related formation of fistula between the rectum and urethra
- Permanent damage to the bladder, trigone or ureteral orifices requiring intervention

If any of the above are noted, a request will be sent to the site to report such event. Copies of the retroperitoneal ultrasound will be available for the CEC if they deem necessary.

15 Training

The Sponsor will be responsible for training appropriate clinical site study personnel. All physicians proctored by the Sponsor, as well as other trained physicians, must have completed the commercial training program. To ensure proper procedural technique, uniform data collection and protocol compliance, the Sponsor will present a formal training session to personnel at each study site. At this training session the Sponsor will review the study protocol, techniques for the identification of eligible subjects, instructions on data collection, schedules for follow-up assessments, and regulatory requirements.

16 Data Management

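### The independent ultrasound review in 14.11 omits hydronephrosis, one of the four primary safety components, and the endpoint gives its grade without the threshold used in exclusion 17

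*Combined protocol and SAP*

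**What the plan says.** **Endpoint.** The synopsis, 9.3.2 and 12.2 each list four components of the device-related composite: perforation of the rectum or GI tract; fistula between rectum and urethra; permanent damage to the bladder, trigone or ureteral orifices requiring intervention; and "Grade 2 hydronephrosis". Section 12.2 tests the 6-month rate against 12% with a one-sided exact binomial test at 5%. It allows at most 5 of 88 subjects (5.7%) with an event. Section 13 makes meeting this endpoint a condition of study success.

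**Eligibility.** Exclusion 17, in the synopsis and in 9.4.2, reads "Hydronephrosis (Grade 2 or higher". No grading scale is named for the criterion or for the endpoint.

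**Independent review.** Under 14.11 a reviewer reads all baseline, 2-week (if applicable) and 6-week "retroperitoneal ultrasounds to assess for any unreported device-related serious complications defined as" three items: perforation, fistula and permanent damage. If one of these is seen, the site is asked to report it. Hydronephrosis is not on the list.

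**The scans.** Section 11.7 uses the ultrasounds to judge the primary safety endpoint, "in particular the presence of permanent damage to the bladder, trigone, or ureteral orifices". It also requires kidney views: "Assessment of the cortices and renal pelvises should be made".

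**The concern.** The reviewer in 14.11 is the check on under-reporting by sites. It covers three of the four components. The one left out is the one for which these ultrasounds are the only scheduled kidney imaging. Perforation and fistula also have the examination, the three questions, the urine culture and a conditional CT (11.8). Bladder, trigone and orifice damage also has recorded cystoscopy reviewed by the CEC (11.4, Table 10-2). Cystoscopy does not image the kidney. A hydronephrosis visible on the 6-week scan but not reported by the site therefore has no written route back through this reviewer.

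The grade wording adds a smaller problem. The same document writes a threshold in exclusion 17 and a single grade in the endpoint, so a literal reader could leave a more severe finding uncounted.

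Both faults act in one direction. The endpoint is met by a low count, so an omitted event can help the trial pass and can never make it fail.

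**Working it through.** **Lists compared.**

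| Component | Composite (12.2) | Reviewer list (14.11) |
|---|---|---|
| Perforation, rectum or GI tract | yes | yes |
| Recto-urethral fistula | yes | yes |
| Permanent bladder, trigone or orifice damage | yes | yes |
| Hydronephrosis | yes (Grade 2) | no |

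**The plan's own limit.** Inputs from 12.2: n = 88, goal 12%, one-sided 5%. With X ~ Binomial(88, 0.12):

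- P(X ≤ 5) = 0.0393, below 0.05, so 5 of 88 (5/88 = 5.7%) passes.
- P(X ≤ 6) = 0.0846, above 0.05, so 6 of 88 (6.8%) fails.

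The stated limit of 5 of 88 reproduces exactly. Counting Grade 2 or higher does not alter it.

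**When one lost subject matters.** If one event subject goes uncounted, the conclusion changes only when the true count is exactly 6. That probability is P(X ≤ 6) − P(X ≤ 5):

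| True composite rate | P(X ≤ 5) | P(X ≤ 6) | P(X = 6) |
|---|---|---|---|
| 12% (the null) | 0.03926 | 0.08461 | 0.04535, or 4.5% |
| 3.0% (assumed) | 0.95070 | 0.98321 | 0.03251, or 3.3% |
| 3.4% (assumed) | 0.92038 | 0.96947 | 0.04909, or 4.9% |

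The 3.4% appears in an unfinished sentence at the end of 12.3. It is not presented there as an expected rate and is used here only as a second low value.

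The P(X ≤ 6) column is the chance of passing if one subject were always lost, so it is an upper bound for a single loss. At the null it is 8.5%, against 3.9% with full counting and a nominal 5%.

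**If a share m of event subjects is missed.** The counted rate becomes p(1 − m). The shares below are assumptions.

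- p = 12%, m = 10%: rate 10.8%, P(X ≤ 5) = 7.6%.
- p = 12%, m = 20%: rate 9.6%, P(X ≤ 5) = 14.0%.
- p = 3.0%, m = 10%: rate 2.7%, P(X ≤ 5) = 96.8%, against 95.1% with none missed.

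The documents give no hydronephrosis rate and no split by grade, so m cannot be estimated.

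**The case against.** The case for leaving the text alone has four parts.

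**The grade is plainly a threshold.** The revision history for Revision 04 records the addition of exclusion 17 in the short form, although the criterion itself carries the threshold. It also records the endpoint moving from Grade 4 to Grade 2, which makes sense only as a widening. Three urologists on the CEC adjudicate. This largely stands: a reader might infer that Grade 3 and 4 events will go uncounted, but the documents do not support that as the intent. What remains is an endpoint whose text should not need interpretation, and an unnamed scale.

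**Section 11.7 already looks at the kidneys.** A reader might infer that the scans are not directed at hydronephrosis because only bladder, trigone and orifice damage is singled out. That goes too far. The request must support "appropriate performance of the ultrasound focusing on the primary safety endpoint criteria listed above", which can be read as reaching the full list in 9.3.2. The renal pelvises must be assessed and abnormalities measured, and new site-reported findings go to the CEC.

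**Worsening from Grade 1 is not lost.** The CEC trigger covers "Any site reported abnormalities present on the 2 week (if abnormal BUN or Creatinine) or 6-week ultrasound that were not present at baseline", and Grade 1 at entry is not excluded, so a reader might infer that progression falls outside it. On a plain reading, Grade 2 in a subject eligible under exclusion 17 was not present at baseline. Section 14 adds: "Pre-existing conditions will not be reported as an AE unless there is an adverse change in that condition". Under 19.1, adverse events possibly related to the device, procedure or disease go to the CEC.

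**Other safeguards exist.** Hydronephrosis is a listed anticipated event (14.4), an abnormal BUN or creatinine at week 2 triggers an extra scan (Table 10-2), and the CEC may ask for the ultrasounds (14.11). These narrow the gap to a finding that is visible on a scan, unreported by the site, and not raised by the independent reader because it is off the list. They do not close it, because most of them depend on the site reporting.

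**Conclusion.** The point holds as a minor internal inconsistency in a primary endpoint. It is not a flaw of design. Section 14.11 omits one of the four components it exists to check, and the endpoint's grade wording does not match exclusion 17.

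The direction of any error is certain; its size is not. One lost event subject reverses the result in at most 4.5% of trials at a true 12% and 3.3% at an assumed 3.0%. For the gap described here, one of those six subjects must also have hydronephrosis as the only composite event and have gone unreported by the site. A reader might infer that the test's error rate really is 8.5%. The documents do not support that: the figure assumes a loss in every trial that has an event, and nothing in the plan says how often a loss would occur.

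**What to change.** 1. Add hydronephrosis to the reviewer's list in 14.11, so that an unreported finding triggers the same request to the site as the other three components.
2. In the synopsis, 9.3.2 and 12.2, reconcile the component with exclusion 17 as hydronephrosis of Grade 2 or higher, and name the grading scale. Do not add a baseline qualifier to the endpoint; the current definition has none.

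Optional, for clarity: name hydronephrosis in 11.7 with its grade recorded, and extend the CEC trigger there to abnormalities that worsened since baseline.

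The cost is wording only. The kidney views are already taken and the reviewer already reads the scans; sample size, limit, alpha and CEC adjudication of device-relatedness stay as they are. The counted event rate may be slightly higher, and the CEC may have a few more findings to adjudicate.

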12.4 Secondary Endpoints

The secondary endpoints include an assessment of IPSS on a continuous scale and additional responder analyses at different follow up time points. All secondary endpoints will be analyzed based on the treated analysis population consisting of subjects treated with the Rezūm System.

For all secondary endpoints based on IPSS scores, treated subjects who chose alternate treatments other than the assigned treatment prior to the end of the endpoint's follow-up period will be considered failures and their baseline value will be used as their imputed follow-up IPSS score for the secondary endpoint analysis.

12.4.1 Secondary Endpoint S1: Device-related retention catheterization rate

This safety endpoint will be to characterize the rate of post procedure device-related serious retention catheterizations at 6 months.

Device-related serious catheterizations for this endpoint are defined as:

- De novo acute severe urinary retention lasting more than 30 cumulative days post treatment

Catheterizations will be adjudicated by the clinical events committee (CEC) for this endpoint.

12.4.2 Secondary Endpoint S2: Absolute IPSS improvement at 6 months

The following hypothesis will be tested in a one-sided one-sample *t*-test at the 2.5% significance level.

$$H_0: \mu_{\text{Rezūm6}} \leq 6.0$$

$$H_1: \mu_{\text{Rezūm6}} > 6.0$$

Where:

$\mu_{\text{Rezūm6}}$ is the mean IPSS improvement at 6 months

The performance goal of a 6.0 point average improvement in IPSS score is derived based on clinical relevance and ensuring response greater than historical sham mean improvement. In the previously conducted Rezūm II study, observed mean improvement in the sham arm at 3 months was 4.3 points. The Rezūm II study required the treatment arm mean to exceed 125% of the mean sham improvement. In order to ensure clinical relevance, an additional 15% is added to the Rezūm II criteria. The minimum performance goal of 6.0 equals 140% of the historical sham mean improvement.

Statistical significance will be claimed when the alternate hypothesis of the secondary endpoint is met based on a one sided type 1 error of 0.025.

If the final number of treated subjects is 88 and the standard deviation of the improvement in IPSS score is 8 points, then the mean improvement in IPSS score at 6 months must be at least 7.1 in order to pass the hypothesis test and conclude that the mean IPSS improvement is statistically significantly greater than 6.0 points.

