Confidential

		
 19. Section 11.7 removed wording of perforation and fistula assessment through retroperitoneal ultrasound 20. Added Section 11.8 Genitourinary Perforation and Fistula Formation to assess perforation and fistula assessment at the 2 and 6 week visits through Abdominal and Pelvic exams, urine culture and CT scan if necessary 21. Section 12.2 added Grade 4 hydronephrosis to the primary safety endpoint list 22. Section 14.0 Definition of Adverse Events – clarified all adverse events will be reported 23. Updated the potentially anticipated adverse event list in section 14.4 24. Section 19.1 Clinical Events Committee – clarified all AEs and SAEs should be reported and adjudicated
04	February 2018	
 1. Added Grade 2 Hydronephrosis as exclusionary criteria #17 2. Modified Prostate cancer testing exclusionary criteria eliminating MRI and PSA Velocity parameter language 3. Modified Primary Safety Endpoint from Grade 4 to Grade 2 Hydronephrosis 4. Clarified section 9.3.3 definition of stopping rule to include the words “hospitalization” and “bladder” 5. Table 10-1 eliminating MRI and PSA velocity parameter language 6. Modified footer #4 in Table 10-2 to include “other exams deemed necessary” 7. Modified Section 10.6 to clarify subjects whom discontinue BPH medications post procedure and resume prior to their 6 month follow-up will be a treatment failure 8. Added language in section 11.8 to allow other evaluations deemed necessary to rule out perforations of the GI or GU 9. Section 12.4.2 Secondary Endpoint S2 performance goal was changed from 5.4 to 6.0 10. Updated 24 month data in Table 8-2 11. Modified exclusion criteria#18 by removing PSA > 10ng/ml unless prostate cancer is ruled out by biopsy

Confidential

05	October 2018	
1. Change US site total from 6 to 10. Totaling 11 active US and AUS sites.2. Remove baseline interval of PGI-I test3. Changed Sponsor name and contact information from NxThera to NxThera, a Boston Scientific Company due to company acquisition4. Addition of mandatory UA prior to procedure5. Standardization of antibiotics pre and post catheterization removal6. Addition of scale of Severity of Adverse Events
----	--------------	---

**Minimally Invasive Prostatic Vapor Ablation -
Multicenter, Single Arm Study for the Treatment
of BPH in Large Prostates
(Rezūm XL)**

CLINICAL STUDY PROTOCOL:

3034-001 Revision 05

October 2018

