9.3.4 Secondary Endpoints

The following secondary endpoints will be statistically assessed to provide additional characterization of the Rezūm System in the treatment of obstructive BPH. Secondary endpoint S2 with prespecified hypotheses and well-controlled Type I error will be used to and to support potential labeling claims. Refer to Section 12.4 for further details.

- Secondary Endpoint S1: Device-related retention catheterization rate
- Secondary Endpoint S2: Absolute IPSS improvement at 6 months
- Secondary Endpoint S3: Percent Responder at 1 year
- Secondary Endpoint S4: Percent Responders at 2 years
- Secondary Endpoint S5: Percent Responders at 3 years

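### Section 12.4.2 gives 7.1 as the mean IPSS improvement that passes the S2 test against 6.0; with the section's own n = 88 and SD 8 the smallest passing mean is 7.7, and 7.1 gives one-sided p = 0.10

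*Combined protocol and SAP*

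**What the plan says.** Section 12.4.2 sets the null hypothesis that the mean 6-month improvement is at most 6.0 points and names the test: "The following hypothesis will be tested in a one-sided one-sample *t*-test at the 2.5% significance level". It repeats the level further down: "Statistical significance will be claimed when the alternate hypothesis of the secondary endpoint is met based on a one sided type 1 error of 0.025".

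The goal is derived from the 4.3-point mean improvement in the Rezūm II sham arm at 3 months: "The minimum performance goal of 6.0 equals 140% of the historical sham mean improvement". The section also recalls the criterion of the earlier trial: "The Rezūm II study required the treatment arm mean to exceed 125% of the mean sham improvement".

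It closes with a worked example. If 88 subjects are treated and the SD of the improvement is 8 points, "then the mean improvement in IPSS score at 6 months must be at least 7.1 in order to pass the hypothesis test". The same sentence names 6.0 as the value to be exceeded.

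On the role of S2, Section 9.3.4 says: "Secondary endpoint S2 with prespecified hypotheses and well-controlled Type I error will be used to and to support potential labeling claims". Section 13 leaves S2 out of the success definition: "The study will be declared a success if the primary efficacy and safety endpoints are met".

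**The concern.** The section fixes everything needed to compute the pass mark: null value, test, one-sided level, sample size and SD. The mark it then prints is only 1.1 points above the null value, which is about 1.3 standard errors. A one-sided 2.5% test needs about 2 standard errors.

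S2 is the only secondary endpoint with a hypothesis test; S1 and S3 to S5 are described as characterizations. The worked example is also the section's only numerical statement of what passing S2 requires, and it is phrased as a requirement. A reader who relies on it would expect a pass at an observed mean of 7.1 to 7.6, where the stated test does not reject at SD 8. If 7.1 were used as the cut-off, the one-sided error rate at a true mean of 6.0 and SD 8 would be about 10%, not 2.5%. A plan that holds two incompatible pass marks invites dispute once the data are known.

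**Working it through.** **Inputs, all from Section 12.4.2:** null value 6.0; one-sided one-sample t-test, α = 0.025; n = 88; SD = 8; stated smallest passing mean 7.1.

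**Smallest passing mean:** null value + t(0.975, n − 1) × SD/√n

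- Standard error: 8/√88 = 0.8528
- t(0.975, 87 df) = 1.9876
- Margin: 1.9876 × 0.8528 = 1.695
- Threshold: 6.0 + 1.695 = **7.695, or 7.7**

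The plan's 7.1 is not reproduced.

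**What the test gives at particular means (n = 88, SD 8):**

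| Observed mean | t = (mean − 6.0)/0.8528 | One-sided p |
|---|---|---|
| 7.1 | 1.290 | 0.100 |
| 7.6 | 1.876 | 0.032 |
| 7.7 | 1.993 | 0.0247 |

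**Could another reading give 7.1 against 6.0?**

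| Variant | Threshold |
|---|---|
| Normal approximation, 2.5% | 7.67 |
| t-test at 5% one-sided (the level used for safety in Section 12.2) | 7.42 |
| t-test, 2.5%, SD 7.6 | 7.61 |
| t-test, 2.5%, SD 7.9 | 7.67 |
| t-test, 2.5%, SD 8.6 | 7.82 |
| t-test, 2.5%, SD 6.9 | 7.46 |
| t-test at 10% one-sided, SD 8 | 7.10 |

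The SDs of 7.6 to 8.6 are those reported for IPSS change at 3 to 24 months in the pilot study (Table 8-2) and at 3 months in the Rezūm II treatment arm (Table 8-6). At those SDs a mean of 7.1 gives p = 0.089 to 0.117. The 6.9 is the Rezūm II control-arm SD at 3 months; with it, 7.1 gives p = 0.069. At 2.5%, a threshold of 7.1 would need an SD of 1.1 × √88/1.9876 = 5.2, or n = 206 at SD 8. Section 9.2 caps the study at 88. Only the 10% level gives 7.1 against 6.0 at SD 8, and the plan uses that level nowhere.

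**Likely origin.** With a goal of 5.4 the same calculation gives 5.4 + 1.695 = 7.095, which rounds to 7.1. In Section 12.4.2, 125% of the sham improvement is 1.25 × 4.3 = 5.375, and 140% is 1.40 × 4.3 = 6.02. The revision history for Rev 04 records: "Section 12.4.2 Secondary Endpoint S2 performance goal was changed from 5.4 to 6.0". The worked figure was probably left behind when the goal changed. The documents do not say so, and the error does not depend on it, since 6.0 and 7.1 stand together in the current text.

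**How often would it matter?** The chance that the observed mean falls between 7.1 and 7.695, at SD 8, n = 88 and with a normal sampling distribution for the mean:

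| True mean | Chance |
|---|---|
| 11.2 (Rezūm II treatment arm, 3 months) | about 0.002% |
| 10 (assumed) | 0.3% |
| 9 (assumed) | 5% |

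**The case against.** The strongest reply is that nothing turns on the number. The hypotheses, the test and the level are complete without it. The sentence is conditional on 88 subjects and an SD of 8, so it is an example and not a decision rule. Study success rests on the two primary endpoints, the sample size is derived from the primary efficacy endpoint, and Section 9.3.4 speaks only of potential labeling claims. If the result resembles the earlier trials, the observed mean will lie far above both 7.1 and 7.7. All of this stands, and it limits the weight of the point. It does not make 7.1 correct under the example's own conditions.

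Three narrower qualifications also stand:

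- A one-sided level of 10% does reproduce 7.1 against 6.0. The section states 2.5% twice, so this is not an available reading.
- The SD range of 7.6 to 8.6 describes treated subjects in the overall study results. The control arm's 6.9 is smaller, and 7.1 still fails with it. All of these SDs are only a guide. The earlier studies enrolled mostly smaller prostates, and it is not shown whether their SDs reflect the Section 12.4 rule that subjects who choose alternate treatment are given their baseline score.
- True means of 9 and 10 are assumptions; the documents do not present them as expected effects.

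**Conclusion.** The concern holds. With the inputs of Section 12.4.2 the smallest passing mean is 7.7, not 7.1. The printed figure is 0.6 points too low and corresponds to one-sided p = 0.10. This rests only on the section's own null value, level, n and SD, and no other SD or significance level given in the plan brings the threshold down to 7.1.

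The consequence is limited. The specified t-test still governs, and neither primary endpoint is affected. The practical risk is small unless the true mean is well below that of Rezūm II. It should still be corrected, because the figure reads as the pass mark for the one secondary endpoint with a formal test.

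**What to change.** In Section 12.4.2, replace the worked figure of 7.1 with 7.7. Add one sentence: This figure is illustrative; the one-sided 2.5% t-test with the observed n and SD decides. The new number alone corrects the error; the sentence settles which statement governs if the final n or SD differs from 88 and 8.

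The cost is one number and one sentence. The test, the sample size, the patients and the data are unchanged.
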